2 STUDY OBJECTIVES AND PURPOSE

2.1 Rationale for the Study

Currently there is no approved medication for the treatment of NASH. Volixibat is under development for the treatment of NASH based on its MOA and is supported by nonclinical and Phase 1 data. This is a Phase 2, 48-week, dose-finding study to examine the efficacy, tolerability, and safety of volixibat in adults with NASH.

2.2 Study Objectives

2.2.1 Primary Objective

To evaluate the effect of volixibat compared to PBO on liver histology

2.2.2 Secondary Objectives

- To evaluate the safety and tolerability of volixibat compared to PBO
- To evaluate the effect of volixibat compared to PBO on hepatic steatosis (measured by MRI)
- To evaluate the effect of volixibat compared to PBO on liver histology (measured by individual NAS components and fibrosis stage)
- To evaluate the effect of volixibat compared to PBO on liver histology (measured by NASH resolution without worsening fibrosis)
- To evaluate the effect of volixibat compared to PBO on serum liver-related biochemistry
- To evaluate the effect of volixibat compared to PBO on metabolic indicators (glucose, insulin, hemoglobin A1c [HbA1c])
- To evaluate the effect of volixibat compared to PBO on serum lipids (cholesterol, HDL-C, LDL-C, triglycerides)

2.2.3 Exploratory Objectives

- To explore the effect of volixibat compared to PBO on liver histology (measured by individual SAF scoring components: Steatosis (S), Activity (A), and Fibrosis (F))
- To explore the effect of volixibat compared to PBO on anthropometric measures (body weight, body mass index (BMI), waist circumference and waist-hip ratio)
- To explore the effect of volixibat compared to PBO on homeostasis model assessment-IR (HOMA-IR) and HOMA-beta cell function (HOMA-%B) in subjects with T2DM
- To explore the effect of volixibat compared to PBO on BA synthesis (7-alpha-hydroxy-4-cholesten-3-one [C4])
- To explore the effect of volixibat on patient-reported health-related quality of life (HRQoL) and overall health status.

3 STUDY DESIGN

3.1 Study Design and Flow Chart

This study will be a Phase 2, 48-week, multicenter, double-blind, randomized, PBO-controlled, parallel group, proof of concept, dose-finding study, with one IA after at least 80 subjects have 24 weeks of treatment. There will be 3 active arms of volixibat (5, 10 and 20 mg) and a PBO arm. Subjects will be randomized to receive one of three doses of volixibat (5, 10, or 20 mg once daily (QD) or PBO in a 1:1:1:1 ratio prior to the IA. After randomization of at least 80 subjects

(20/treatment arm), a 24-week IA may eliminate at least one volixibat dose group based on the criteria provided to the Data Monitoring Committee (DMC). Following the IA, enrollment will continue in order to achieve the sample size target of 67 completers in each of the treatment groups that were not dropped at the IA (201 total if 3 arms continue, 134 if 2 arms continue). Accounting for a 20% dropout, 81 subjects will be randomized in each of the treatment groups that continue. Including the projected approximately 49 additional subjects randomized to a dose that is dropped at the IA, 292 subjects (81 for each arm that continues + approximately 49 in the dropped arm) will be randomized if 3 arms (2 volixibat and 1 PBO) continue; 260 subject (81 for each arm that continues + approximately 49 for each of the dropped arms) will be randomized if 2 arms (1 volixibat and 1 PBO) continue. Should the number of subjects randomized prior to the IA to a dose group that is dropped at the IA markedly deviate from the above projection, then the total number of subjects randomized will be adjusted accordingly, not to exceed approximately 324 subjects. Subjects with fibrosis stages F0 through F3 may be enrolled, but the number of F0 subjects will be capped at 88 if 1 dose is dropped after the IA and at 78 if 2 doses are dropped after the IA (approximately 30% of the total number of subjects randomized).

[figure not shown]
There will be up to 3 study periods (screening, treatment, and follow-up) and an IA. The duration of the Treatment period will be 48 weeks, with an IA at Week 24. Depending on the results of the IA, the study may be terminated or the randomization to one or more doses may be stopped. The follow-up period will be 4 weeks after last dose. Subjects will be expected to visit the study center at least 10 times.

The IA will be conducted by an independent DMC after at least 80 subjects have received 24 weeks of treatment. The IA will evaluate the safety, tolerability and efficacy of 3 doses of volixibat each compared to PBO.

Once decisions as to dose elimination are made, additional sites may be added. Subjects recruited into the study prior to the IA will continue with the same dosing regimen for the duration of the planned study participation. Subjects recruited into the study after completion of the IA will be randomized evenly to the remaining dose groups (noted by “[1 or 2]... Dose TBD” in [Figure 1](#)) or PBO group by IRT. Thus, depending on the results from the IA, the study may be terminated, or one or more doses of volixibat may be discontinued. If the study is not terminated, subjects will receive a total of 48 weeks of investigational product (IP).

The study will be conducted over 3 periods: screening (10 weeks), treatment (48 weeks), and follow-up (4 weeks), with an IA at 24 weeks as outlined in [Figure 1](#).

Figure 1 Study Design Flow Chart

3.2 Duration and Study Completion Definition

The subject's maximum duration of participation is expected to be approximately 434 days. The last visit is an in-clinic safety follow-up visit. The study will be completed in approximately 4 years.

The Study Completion Date is defined as the date the final subject, across all sites, completes their final protocol-defined assessment. Please note that this includes the follow-up visit. The Study Completion Date is used to ascertain timing for study results posting and reporting.

3.3 Sites and Regions

This study will be conducted at approximately 60 to 80 clinical sites in the USA, Canada, and EU.

4 STUDY POPULATION

Each subject must participate in the informed consent process and provide written informed consent before any procedures specified in the protocol are performed.

4.1 Inclusion Criteria

The subject will not be considered eligible for the study without meeting all of the criteria below.

1. An understanding, ability, and willingness to fully comply with study procedures and restrictions.
2. Ability to voluntarily provide written, signed, and dated (personally or via a legally authorized representative, as applicable) informed consent to participate in the study.
3. Age 18-80 years inclusive. This inclusion criterion will only be assessed at the first screening visit.
4. Male, or non-pregnant, non-lactating female, who is sexually active and who agrees to comply with the contraceptive requirements of the protocol, or females of non-childbearing potential. Males and females of child-bearing potential who are sexually active must agree to use acceptable contraception during the study and for 30 days following the last dose of the IP as described in Section 4.4.
5. Presence of $\geq 5\%$ steatosis on screening MRI from a centrally read radiologist performed either during the screening period or within 6 months prior to the first visit.
6. Histologic confirmation of NASH without cirrhosis (F0-F3) from a centrally read liver biopsy performed either during the screening period or within 6 months prior to the first visit with a NAS of ≥ 4 with a score of at least 1 in each component (steatosis, lobular inflammation, and hepatocyte ballooning).

4.2 Exclusion Criteria

Subjects are excluded from the study if any of the following exclusion criteria are met.

1. Presence of or history of cirrhosis or evidence of decompensated liver disease (ie, ascites, variceal bleeding, etc.) or hepatocellular carcinoma.
2. History or presence of other concomitant liver disease as assessed by the investigator or determined by laboratory findings including, but not limited to: active hepatitis B virus (HBV) infection (hepatitis B surface antigen [HBsAg] positive and/or HBVDNA positive; subjects who are hepatitis B core antibody [HBcAb] positive may be eligible as long as HBsAg is negative and HBVDNA is nondetectable), active hepatitis C virus (HCV) infection (prior exposure to HCV [defined as HCVAb positive] without a current or prior history of a detectable HCVRNA) may be eligible, alcoholic liver disease, proven autoimmune hepatitis, primary biliary cirrhosis (PBC), primary sclerosing cholangitis (PSC), hemochromatosis, Wilson's disease, alpha-1 antitrypsin deficiency, bile duct obstruction, liver primary or metastatic cancer.
3. Current or recurrent disease that could affect the action, absorption, disposition, or laboratory assessment of the investigational product (IP) (including bile salt metabolism in the intestine) eg, uncontrolled inflammatory bowel disease, uncontrolled celiac disease, gastric bypass procedures (gastric lap band or gastric sleeve is acceptable), ileal or ileocecal resection, uncontrolled irritable bowel syndrome with predominant diarrhea, or history of chronic diarrhea or loose stools of any etiology.
4. Weight change $\geq 5\%$ after qualifying liver biopsy and/or MRI performed. If the subject had a liver biopsy and/or MRI within 6 months of screening, but experienced a weight change of

$\geq 5\%$ since the date of liver biopsy and/or MRI, the liver biopsy and/or MRI must be repeated at screening.

5. Contraindications to MRI (eg, claustrophobia, coronary stents, coronary implantable devices, girth, etc.). Stents or other devices may be allowed, at the investigator's discretion, if they do not interfere with the functioning of the MRI machine.
6. Current or relevant history of physical or psychiatric illness, any medical disorder that may require treatment or make the subject unlikely to complete the study.
7. Treatment with Vitamin E, thiazolidinediones (TZD), or glucagon-like peptide-1 receptor agonists (GLP-1 RA) unless subject on a stable dose for 6 months prior to qualifying liver biopsy and not initiated after qualifying liver biopsy and will continue the same dosing regimen throughout study participation (refer to Section [5.2.1](#), Permitted Treatment).
8. Uncontrolled diabetes defined as HbA1c of $\geq 9.5\%$ within 60 days prior to enrollment.
9. Current use of any medication (including over-the-counter, herbal, or homeopathic preparations) that could affect the action, absorption, or disposition of the IP, or clinical or laboratory assessment. (Current use is defined as use within 14 days of screening). Patients currently taking insulin will not be excluded; however, they must be on a stable dose for at least 30 days prior to screening, or a sliding scale of insulin is allowed as long as the subject's HbA1c remains $< 9.5\%$. Also refer to Section [5.2.2](#), Prohibited Treatment.
10. Use of drugs, herbs or supplements historically associated with causing or worsening NAFLD/NASH for less than 6 months prior to liver biopsy, or initiated any time after liver biopsy performed, including the use of total parenteral nutrition (TPN). Also refer to Section [5.2.2](#), Prohibited Treatment.
11. Serum AST > 7 times upper limit of normal (ULN) at screening.
12. Serum ALT > 7 times ULN at screening.
13. Elevated serum creatinine ≥ 2.0 mg/dL.
14. International normalized ratio (INR) > 1.3
15. TB > 2 times ULN at screening (Except for documented Gilbert's syndrome with bilirubin levels 20 μ mol/L to 90 μ mol/L (1.2 to 5.3 mg/dL) and with a ratio of unconjugated/conjugated bilirubin that is commensurately higher).
16. Platelet count $< 130 \times 10^9/L$
17. Medical history of impaired hemostasis or use of anticoagulant medication (use of antiplatelet medications, such as low-dose, ie 81 mg, aspirin (ASA) or clopidogrel (Plavix) will be allowed).
18. Uncontrolled thyroid disease.
19. Type 1 diabetes mellitus.
20. Known or suspected intolerance or hypersensitivity to the IP, closely-related compounds, or any of the stated ingredients.

21. Known history of alcohol or other substance abuse within the last year or at any time during the study based on investigator's discretion. Refer to Section 7.2.3.8, Drug and Alcohol screening. Weekly alcohol intake greater than 21 grams/day for males and 14 grams/day for females on average or inability to reliably quantify alcohol consumption based on investigator's judgment.
22. Within 6 months of MRI and liver biopsy:
 - Have used any IP
 - Have been enrolled in a clinical study (including vaccine studies) that, in the investigator's opinion, may impact this Shire-sponsored study
23. Inability to safely obtain a liver biopsy.
24. Females who are pregnant, planning to become pregnant, or are breastfeeding, or males who are planning to father a child during study participation.
25. The anticipated need for a surgical procedure during the study that could interfere with the treatment.
26. Known positivity for human immunodeficiency virus (HIV) infection.
27. Cancer within 5 years of screening, except for basal or squamous cell carcinoma of the skin or in situ cervical carcinoma that has been treated with no evidence of recurrence.
28. History of noncompliance with medical regimens, unreliability, mental instability or incompetence that could compromise the validity of informed consent or lead to noncompliance with the study protocol.
29. Any other conditions or abnormalities which, in the opinion of the investigator, may compromise the safety of the subject, or interfere with the subject participating.
30. Subject is currently enrolled in this study at any study site (unless the subject is transferring to another qualified study site with prior sponsor approval).
31. Subjects who are employees at the unit of the investigational site that is conducting the study.

4.3 Restrictions

Subjects must adhere to the following restrictions for the duration of the study:

- Subjects must remain compliant with inclusion/exclusion criteria.
- Subjects should not become pregnant, father a child, or nurse/breastfeed a baby.
- Subjects should be encouraged to adhere to the same exercise routine and a healthy diet throughout the study.

4.4 Reproductive Potential

4.4.1 Female Contraception

Sexually active females of child-bearing potential should use an acceptable form of contraception. Females of child-bearing potential must be advised to use acceptable contraceptives throughout the study period and for 30 days following the last dose of the IP. If hormonal contraceptives are used they should be administered according to the package insert.

Female subjects should be either:

- Post-menopausal (12 consecutive months of spontaneous amenorrhea and age ≥ 51 years)
- Surgically sterile (having undergone one of the following surgical acts: hysterectomy, bilateral tubal ligation, bilateral oophorectomy, or bilateral salpingectomy) and at least 6 weeks post-sterilization, or
- Females of child-bearing potential with a negative urine and/or serum β -human chorionic gonadotropin (β -HCG) pregnancy test each study visit. Females of child-bearing potential must agree to abstain from sexual activity that could result in pregnancy or agree to use acceptable methods of highly-effective contraception.

Acceptable methods of highly-effective contraception (ie, methods that result in a failure rate of <1% per year) are:

- Combined (estrogen and progestogen containing) hormonal contraceptives associated with inhibition of ovulation (oral, intravaginal, transdermal) stabilized for at least 30 days prior to the screening visit (Visit 1) plus a barrier method (eg, condoms or diaphragms with spermicidal gel or foam)
- Progestogen-only hormonal contraception associated with inhibition of ovulation plus a barrier method
- Intrauterine device (IUD)
- Intrauterine hormone-releasing system (IUS)
- Bilateral tubal occlusion
- Male sterilization/vasectomized partner
- True abstinence: When this is in line with the preferred and usual lifestyle of the subject (Periodic abstinence [eg, calendar, ovulation, symptothermal, post-ovulation methods], declaration of abstinence for the duration of exposure to IMP, and withdrawal are not acceptable methods of contraception.)

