25. The anticipated need for a surgical procedure during the study that could interfere with the treatment.
26. Known positivity for human immunodeficiency virus (HIV) infection.
27. Cancer within 5 years of screening, except for basal or squamous cell carcinoma of the skin or in situ cervical carcinoma that has been treated with no evidence of recurrence.
28. History of noncompliance with medical regimens, unreliability, mental instability or incompetence that could compromise the validity of informed consent or lead to noncompliance with the study protocol.
29. Any other conditions or abnormalities which, in the opinion of the investigator, may compromise the safety of the subject, or interfere with the subject participating.
30. Subject is currently enrolled in this study at any study site (unless the subject is transferring to another qualified study site with prior sponsor approval).
31. Subjects who are employees at the unit of the investigational site that is conducting the study.

Maximum duration of subject involvement in the study:

- Planned duration of screening period: 70 days
- Planned duration of treatment period: 336 days
- Planned duration of follow-up: 28 days

Endpoints and statistical analysis:

Safety Analysis Set will consist of all subjects who take at least 1 dose of randomized IP, and have at least 1 post-baseline safety assessment (eg, coming back for any visit, reporting of an adverse event (AE) or reporting the absence of AEs).

Full Analysis Set (FAS) will consist of all subjects in the Safety Analysis Set who have at least 1 post-baseline efficacy assessment (eg, MRI, liver biopsy, serum liver-related biochemistry measurement).

Interim Analysis Set (IAS) will consist of all subjects in the Safety Analysis Set who have at least 1 post-baseline efficacy assessment (eg, MRI, ALT biochemistry measurement) on or before the Week 24 visit at the time of the data cut for the IA.

Screened Set will consist of all subjects who have signed an informed consent.

Randomized Set will consist of all subjects in the Screened Set who have been randomized into the study.

Efficacy Endpoints:

- **Primary:** Binary response indicating (yes/no) whether a subject responded at Week 48 with a reduction of at least 2 points without worsening of fibrosis from baseline NAS.
- **Secondary:**
 - Change from baseline to Week 48 on liver histology as measured by the individual NAS components (ballooning, inflammation, steatosis).

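### Section 4.4.1 accepts any agreement to abstain from a female of child-bearing potential, but its own list of methods rejects abstinence promised only for the trial

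*Protocol*

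**What the plan says.** Section 4.4.1 deals with abstinence in two places.

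- The rule for females of child-bearing potential is that they "must agree to abstain from sexual activity that could result in pregnancy or agree to use acceptable methods of highly-effective contraception".
- The list of highly effective methods that follows includes abstinence with a condition, "True abstinence: When this is in line with the preferred and usual lifestyle of the subject", and adds that a "declaration of abstinence for the duration of exposure to IMP, and withdrawal are not acceptable methods of contraception".

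The section opens by placing the duty to use contraception on sexually active females of child-bearing potential.

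Inclusion criterion 4, in Section 4.1 and the synopsis, admits males, or a non-pregnant, non-lactating female "who is sexually active and who agrees to comply with the contraceptive requirements of the protocol, or females of non-childbearing potential". Its second sentence requires contraception of males and of females of child-bearing potential who are sexually active, during the study and, in the Section 4.1 wording, "for 30 days following the last dose of the IP as described in Section 4.4".

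Section 4.3 makes this a continuing requirement: "Subjects must remain compliant with inclusion/exclusion criteria". Section 3.3 plans "approximately 60 to 80 clinical sites in the USA, Canada, and EU".

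**The concern.** This is an eligibility and safety rule that many sites must apply in the same way. A site that follows the sentence in 4.4.1 could enrol a woman who uses no contraception, on a promise that the list a few lines below rejects. A site that follows the list would refuse her or ask her to use another method.

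If such a woman became pregnant, Sections 4.5.1 and 8.1.7 require her withdrawal, and Section 4.5 says that subjects who discontinue are not replaced. The stake is therefore uneven entry decisions and an avoidable risk of pregnancy on study drug. No test, endpoint or power figure is involved.

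**Working it through.** No arithmetic applies. The check sets the current (Amendment 4) texts side by side and traces individual women through them.

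**The two rules**

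- Sentence: abstain, *or* use a listed method. No condition is placed on usual lifestyle or on the period.
- List: abstinence is itself one of the methods, it must be the woman's usual way of life, and a declaration covering exposure does not count. Exposure here means the treatment period (synopsis: "Planned duration of treatment period: 336 days").

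An agreement to abstain made in order to enter a trial is, in substance, a declaration for the exposure period. The sentence accepts it and the list does not.

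**Cases**

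| Woman | Sentence in 4.4.1 | List in 4.4.1 | Inclusion 4 |
|---|---|---|---|
| A. Child-bearing potential, normally sexually active, promises to abstain for the trial, no other method | Accepts | Rejects | Requires compliance with Section 4.4, so inherits the conflict |
| B. Child-bearing potential, abstinent by usual lifestyle | Accepts | Accepts | First sentence, read literally, has no branch for her |
| C. Child-bearing potential, not currently sexually active, abstinence not her usual lifestyle, no other method | Accepts if she agrees to abstain | Rejects | Second sentence places no contraceptive duty on her, nor does the opening of 4.4.1 |
| D. Abstinent, not of child-bearing potential | Not addressed to her | Not addressed to her | Admitted |

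Case A is the contradiction. Case B is a secondary slip in inclusion 4. Case C shows that changing the sentence alone would not be enough: the opening of 4.4.1 and the second sentence of inclusion 4 would still tie the duty to current sexual activity, while the new sentence would not. Case D shows that the slip in inclusion 4 reaches only women of child-bearing potential.

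**Safeguards already present**

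- Section 7.2.3.7 schedules urine pregnancy tests for females of child-bearing potential at screening, baseline, each treatment visit (Visits 3 to 9) and the final visit: 1 + 1 + 7 + 1 = 10 tests, with serum confirmation of a positive result.
- Exclusion 24 bars women who plan to become pregnant.
- Section 4.3 says that subjects should not become pregnant.
- Section 1.2 describes virtually no systemic exposure to the drug.

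**The case against.** The best reply is that the bullet on true abstinence defines what abstaining means in the earlier sentence. It is the more specific text, it sits in the same section, and the summary of changes for an earlier amendment says that the list was revised to match highly effective methods. On that reading there is one rule, loosely worded.

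Part of this stands. It shows which text is the considered standard, and so which one should give way. It does not remove the conflict. The sentence separates abstaining from the listed methods with *or*, while the list makes abstinence one of those methods. If the bullet governed, the first half of the sentence would have no work to do.

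The safeguards are also a fair answer on size, with one limit: pregnancy tests detect a pregnancy and do not prevent one. After Week 12 the scheduled visits are 12 weeks apart (Weeks 12, 24, 36 and 48).

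Three stronger readings are tempting, and the protocol does not support them.

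- A reader might infer that inclusion 4 shuts out abstinent women. It admits women of non-childbearing potential whatever their sexual activity. For the others, its second sentence and the opening of 4.4.1 show that sexual activity was meant to condition the duty to use contraception, not entry to the trial.
- A reader might add the 30 days after the last dose to the treatment period and present the sum as the span of the rejected promise. The bullet speaks of exposure to the product only.
- A reader might infer a material safety gap. Given the tests, exclusion 24 and the described lack of systemic exposure, the text does not show one.

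**Conclusion.** The point holds as an internal inconsistency in Section 4.4.1: the operative sentence admits a woman of child-bearing potential whom the section's own list rejects. The wording of inclusion 4 is a lesser slip, and clearly unintended.

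The size is small. How many women would offer a trial-only promise cannot be worked out from the protocol, and sample size, power, type I error and the analyses are unaffected. The conclusion assumes that an agreement to abstain given at entry is the kind of declaration the bullet has in mind, which is the natural reading of both texts. It is worth correcting because the rule governs entry and safety at many sites and the correction costs almost nothing.

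**What to change.** 1. In Section 4.4.1, replace the abstain-or-use sentence with: *Females of child-bearing potential must agree to use one of the acceptable methods of highly-effective contraception listed below (which include true abstinence as defined there).*
2. Align the opening sentence of 4.4.1 and the second sentence of inclusion 4 (Section 4.1 and synopsis), so that the duty falls on all females of child-bearing potential, with true abstinence counting as a listed method. The condition of sexual activity stays for males.
3. As a secondary tidy-up, delete the first five words of "who is sexually active and who agrees to comply with the contraceptive requirements of the protocol, or females of non-childbearing potential" from inclusion 4 in Section 4.1 and the synopsis.

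With these edits, women A and C must use another listed method, woman B is eligible under both sections, and woman D and all males are unaffected.

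The cost is a few sentences in the next amendment, with no added visit, test or procedure and no change to sample size or analysis.
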